2.2 Secondary Objective

The secondary objective of this study is:

- To evaluate the safety of Afrezza administered at 2 different doses, combined with basal insulin, in adults 18 years and older with T1DM or T2DM, as measured by:
 - Event rates and incidence of Level 1 (<70 mg/dL) and Level 2 (<54 mg/dL) hypoglycemic events within the 120 minutes after Afrezza dosing
 - Event rates and incidence of severe hypoglycemic events, defined as events requiring assistance of another person to actively administer carbohydrate, glucagon, or other resuscitative actions within the 120 minutes after Afrezza dosing
 - Change in percent predicted forced expiratory volume in 1 second (FEV₁) from before Afrezza dosing to 120 minutes after Afrezza dosing
 - Incidence and severity of adverse events (AEs): treatment-emergent adverse events (TEAEs), serious AEs (SAEs), and AEs of special interest (AESIs)

3 INVESTIGATIONAL PLAN

3.1 Overall Study Design and Plan

MKC-TI-191 is a Phase 4, single-arm, multicenter clinical trial evaluating the efficacy and safety of Afrezza, administered according to the current Afrezza PI compared to a titrated dose, in combination with a basal insulin in adult subjects (≥ 18 years of age) with T1DM or T2DM.

Eligible subjects will be on a stable regimen consisting of a basal-bolus insulin therapy prior to screening.

The study is composed of up to 4 clinic visits (screening, 2 treatment visits, and a follow-up visit):

- **Screening (Visit 1):** Informed consent will be obtained and eligibility confirmed. Eligible subjects will be enrolled at Visit 1.
- **Visit 2:** The first dose of Afrezza will be based on the dose of SC RAA that the subject would normally take, converted according to the guidelines provided in the current Afrezza PI. If the subject's normal RAA dose is <4 units, the subject will be asked to consume enough nutritional shake, per their normal insulin:carbohydrate ratio, to cover an RAA dose of ≥ 4 units such that their Afrezza dose at Visit 3 is higher than the dose taken at Visit 2. After completing the standardized meal challenge, the Investigator will decide, based on the subject's glucose excursion at Visit 2, if the subject should proceed to Visit 3 where a second dose of Afrezza will be administered.
- **Visit 3:** The second dose of Afrezza will be based on the dose of SC RAA that the subject would normally take, converted by multiplying their RAA dose by 2 and rounding down to the nearest Afrezza cartridge size.
- **Follow-up Visit (Visit 4):** Subjects will return for safety assessments, including a final FEV₁ measurement, 24 to 72 hours after their last dose of Afrezza.

See Section 3.5 for information on the assessments to be performed at these visits.

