1.2 Study Rationale

The current study aims to evaluate 2 different doses of Afrezza in adults ≥ 18 years of age. Subjects will administer an Afrezza dose based on the current prescribing information (PI) with a meal challenge, and then proceed to a second meal challenge where a second Afrezza dose will be administered based on the subject's RAA dose multiplied by 2 and rounded down to the nearest Afrezza cartridge size, subject to Investigator discretion.

Pooled Afrezza trial data suggests that subjects achieve similar glycemic control with a dose ratio of 1.5- to 2-fold the equivalent unit value of a SC insulin analog in head-to-head comparisons (Kendall et al. 2020, Grant et al. 2019). Thus, the Sponsor has chosen to evaluate 2 different doses of Afrezza to assess whether a higher dose results in improved postprandial glucose control.

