3.2 Study Duration

Two individual doses of Afrezza will be administered during the study, during Visits 2 and 3. The duration of each subject's participation in the trial is expected to be approximately 2 weeks.

The end of the clinical study is defined as the day the last subject completes his/her last visit. The length of the entire study (from the first subject enrolled to the last subject last visit) is expected to be approximately 3 months.

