3.4.3 Treatment Assignment

All subjects in this study will receive Afrezza at Visits 2 and 3.

Subjects in this study will be assigned a unique subject identification number. Once screening procedures are complete, eligible subjects will be enrolled.

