The AfreZZa dose to be taken at Visit 2 will be based on the dose of RAA that the subject would normally take, converted according to the guidelines provided in the current AfreZZa PI as shown in Table 3.

For AfreZZa doses exceeding 12 units, inhalations from multiple cartridges are necessary. To achieve the required total mealtime dose, subjects should use a combination of 4-unit, 8-unit, and 12-unit cartridges.

Table 3: Dose of AfreZZa at Visit 2

RAA Dose (Units)	AfreZZa Dose (Units)
Up to 4	4
5	8
6	
7	
8	
9	12
10	
11	
12	
13	16
14	
15	
16	
17	20
18	
19	
20	
21	24
22	
23	
24	

RAA=rapid-acting insulin analog (e.g., insulin aspart or insulin lispro)

Note: There is no maximum dose of AfreZZa and the required total mealtime dose may differ from the examples provided in this table.

The dose of AfreZZa will be administered at the start of the meal challenge. The subject must consume 1 to 2 bottles of nutritional shake within 15 minutes for the meal challenge and take SMBG measurements 15 minutes before their AfreZZa dose, immediately before administering the AfreZZa dose ($t=0$; baseline) and at 15, 30, 45, 60, 90, and 120 minutes after AfreZZa dosing. The subject will remain under clinical supervision for the 2 hours after their dose of AfreZZa.

If the subject is wearing a continuous glucose monitor (CGM), they will be asked to write down their CGM value every time they take an SMBG measurement in the clinic. These CGM values will be entered in the CRF completed at Visit 2.

After completing the standardized meal challenge, the Investigator will decide, based on the subject's glucose excursion at Visit 2 if the subject should proceed to Visit 3 where a titrated dose of AfreZZa will be administered according to [Table 4](#).

3.5.2.2.2 Visit 3

The following procedures will be performed at Visit 3:

- Record concomitant medications (see Section [3.4.7.2](#))
- Complete refresher training on the Afrezza inhaler using BluHale PRO
- Measure and record FEV₁ before Afrezza dose
- Take the dose of Afrezza with standardized meal challenge according to Section [3.5.2.2.1.1](#)
- Measure and record FEV₁ after completion of the meal challenge
- Record AEs
- Collect and review glucose meter data
- Record any hypoglycemic episodes (see Section [3.5.5.6](#))
- Provide discharge instructions to the subject

3.5.2.2.2.1 Standardized Meal Challenge and Afrezza Dosing at Visit 3

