5.2.1 General Considerations

All statistical processing will be performed using the most current version of SAS® software (SAS Institute Inc, Cary, NC) at the time of the analysis. Summary tables (descriptive statistics and/or frequency tables) will be provided for screening and/or baseline variables, efficacy variables, and safety variables. Continuous variables will be described by descriptive statistics (n, mean, median, standard deviation, minimum, and maximum). Frequency counts and percentage of subjects within each category will be provided for categorical data.

Individual data will be listed and sorted by treatment, subject identification number, visit, and time point.

Database lock will occur upon the completion of the study.

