5.2.4 Analysis Populations

All subjects in the clinical study who receive a dose of AfreZZa will be included in the analyses reported at the end of the study.

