5.2.6 Subject Disposition

Disposition (the number and percentage of subjects completed or discontinued from the study) will be summarized by visit and/or study period. Reasons for discontinuation will also be summarized.

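### Entry to Visit 3 rests on a judgement of the Visit 2 glucose excursion with no stated criterion, yet SMBG is summarised only by visit, so the two dose columns may describe different people

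*Combined protocol and SAP*

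**What the plan says.** **The decision.** The Synopsis, Section 3.1 and Section 3.5.2.2.1.1 all make Visit 3 conditional. Section 3.1 says "the Investigator will decide, based on the subject's glucose excursion at Visit 2, if the subject should proceed to Visit 3", and the procedures section repeats that the Investigator decides "if the subject should proceed to Visit 3 where a titrated dose" is given. Section 1.2 adds that the second dose is at the Investigator's discretion. None of these places states a criterion. The excursion is also the primary measure: Section 2.1 takes mean change in SMBG from t=0 to six time points up to 120 minutes.

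**Statements that assume everyone is dosed twice.** Section 3.2: "Two individual doses of Afrezza will be administered during the study, during Visits 2 and 3". Section 3.4.3: "All subjects in this study will receive Afrezza at Visits 2 and 3". Section 3.1, by contrast, allows for up to four visits.

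**The aim.** Section 1.2 says the two doses are evaluated "to assess whether a higher dose results in improved postprandial glucose control", and Section 3.1 describes the label-based dose as being compared with a titrated one.

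**The analysis.** Section 5.2.4 includes all subjects "who receive a dose of AfreZZa will be included in the analyses reported at the end of the study". Section 5.2.11 summarises SMBG values by visit and time point (n, mean, median, SD, minimum, maximum) and graphs them. Section 5.2.1 adds that "Individual data will be listed and sorted by treatment, subject identification number, visit, and time point". Section 5.2.6 counts completers and discontinuations by visit or period, and "Reasons for discontinuation will also be summarized".

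**Replacement.** The Synopsis and Section 3.3 let non-completers be replaced. Section 3.3.4 says subjects who discontinue are not.

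**The concern.** The same measurement decides who receives the second dose and serves as the outcome for the first. Once anyone is held back on that basis, the Visit 2 column holds everyone and the Visit 3 column a selected subset. A reader who subtracts one from the other, which is the natural way to answer the question in Section 1.2, gets dose effect plus selection and cannot separate them. Because no criterion is stated, even the sign of the selection part is open.

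Two further points affect what can be read from the tables. Section 5.2.11 plans values, whereas the objective in Section 2.1 is change from t=0. The conflicting statements on who is dosed twice and on replacement leave the size of each column undetermined.

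**Working it through.** **1. What the documents fix.** Section 5.2.3 gives 20 completers and says the number was not statistically derived, so there is no planned figure to reproduce. There is no SD, between-visit correlation or expected share held back. What follows is an illustration, and every input except the 20 is an assumption.

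**2. Column sizes.** With replacement, 20 completers and a share q held back need 20/(1-q) dosed at Visit 2: 23, 25 or 29 (rounded up) against 20 at Visit 3, for q = 10, 20, 30%. Without replacement, 20 dosed at Visit 2 leave 18, 16 or 14.

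**3. Size of the selection effect.** Let Y2 and Y3 be the excursions at the two visits, in SD units, with correlation rho and no dose effect. The decision follows Y2 plus judgement noise of SD tau, and the lowest share q is held back.

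- Shift in Y2 among those who proceed: s = phi(z_q)/(1-q)/sqrt(1+tau²)
- Visit 3 column minus Visit 2 column: rho × s
- Same-subject difference in those who proceed: -(1-rho) × s

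For q = 0.2, phi(z_q) = 0.280, so s = 0.280/0.8 = 0.350 with no noise and 0.350/1.414 = 0.247 with tau = 1. At rho = 0.5:

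| Held back | By-visit, sharp rule | By-visit, noisy rule (tau = 1) | Same-subject |
|---|---|---|---|
| 10% | +0.097 | +0.069 | same size, minus sign |
| 20% | +0.175 | +0.124 | same size, minus sign |
| 30% | +0.248 | +0.176 | same size, minus sign |

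At 20% with the noisy rule, correlations of 0.3 and 0.7 give by-visit shifts of +0.074 and +0.173, and same-subject shifts of -0.173 and -0.074. If SD were 40 mg/dL (assumed), 0.124 to 0.175 SD is about 5 to 7 mg/dL.

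**4. Against sampling error.** Simulation with 20 dosed, 20% held back and rho = 0.5 gives these ratios of bias to standard error:

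- By-visit: 0.177/0.280 = 0.63 (sharp) and 0.122/0.266 = 0.46 (noisy)
- Same-subject: 0.174/0.238 = 0.73 (sharp) and 0.125/0.246 = 0.51 (noisy)

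At the extremes the ratio passes one. With 30% held back and a sharp rule, it is 0.348/0.265 = 1.31 by visit at rho 0.7, and 0.349/0.290 = 1.20 same-subject at rho 0.3.

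**5. Direction.** Holding back low excursions makes the higher dose look worse by visit and better in the same subjects. Holding back the highest 20% reverses both signs (-0.175 and +0.175 with a sharp rule). Holding back 10% at each end gives a net bias of about zero, as does holding back nobody.

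**6. Precision of a paired difference.** The 95% half-width is t(n-1) × sqrt(2(1-rho)/n). At rho = 0.5 it is 0.497, 0.533 and 0.577 SD for n = 18, 16 and 14. This ignores the small change in variance that selection causes.

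**7. Paired difference against a likelihood-based repeated-measures estimate.** Suppose the decision also draws on unrecorded information about the Visit 3 response, with weight w on the standardised Visit 3 residual (20% held back, rho 0.5, sharp rule).

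| w | Paired bias (SD) | Model bias (SD) |
|---|---|---|
| -0.5 | -0.292 | -0.203 |
| 0 | -0.175 | 0.000 |
| 0.5 | -0.02 | +0.19 to +0.20 |

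The ranking changes with w, which nobody will know.

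**8. Dose pairs.** Tables 3 and 4 both give 8 units for an RAA dose of 5, so some pairs may contain no dose difference.

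**The case against.** The strongest reply is that this is a single-arm, proof-of-concept study of 20 completers with no test and no interval, and that its objective (Section 2.1) is mean change at each dose, not a difference. That stands, and it limits the weight of the point. It does not remove it, because Sections 1.2 and 3.1 set up the comparison.

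It can also be said that the plan already exposes the issue: n appears in each column, disposition is summarised by visit with reasons, and the listings give every pair. This stands in part. Nothing is lost from the data, but a listing is not a planned summary.

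Sections 3.2 and 3.4.3 can be read as loose descriptions of a single-arm design, so the conflict with Section 3.1 is weak, though real. On disposition, a held-back subject can be coded under Other, or sometimes Adverse Event, in Section 3.3.3.1. Since Section 3.3.3 requires the treatment visits, such a subject most naturally is not a completer. What is missing is a specific reason, not any place to record the event.

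Finally, the paired contrast is itself affected by the selection, through regression to the mean. That is correct and has to be stated with the result.

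**Conclusion.** The point holds as a gap in the text: entry to Visit 3 depends on the primary measure with no stated criterion, and the planned by-visit summary cannot separate dose effect from selection if anyone is held back. It is a minor, inexpensive improvement to a descriptive study.

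A reader might infer that the dose comparison will be materially biased. The documents do not support that. They do not say that anyone will be held back, how many, or at which end of the range. Under the assumed 20% held back and correlation 0.5, the shift is 0.12 to 0.17 SD, below one standard error, and it is zero if all proceed.

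A reader might also infer that a paired estimate cures the problem, or is less biased than a repeated-measures model. Neither follows. At correlation 0.5 the paired bias equals the by-visit bias with opposite sign, and the ranking against the model depends on what unrecorded information enters the decision.

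**What to change.** Leave the Investigator's decision unchanged and add the following.

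1. Tabulate Visit 2 SMBG change from t=0, and hypoglycaemia, separately for subjects who did and did not proceed, beside Visit 3.
2. Report the within-subject Visit 3 minus Visit 2 difference in SMBG change from t=0, with a confidence interval, in subjects dosed at both visits. State its limits: regression to the mean (opposite in sign to the by-visit bias), fixed visit order, and pairs with no dose difference. Show how many such pairs there are, and reconcile Tables 3 and 4 with the stated aim of a higher dose at Visit 3.
3. Record the Investigator's decision not to proceed as its own disposition reason.
4. Reconcile Section 3.1 with Sections 3.2 and 3.4.3, and Section 3.3 with Section 3.3.4, because they set the denominators.

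A likelihood-based repeated-measures estimate using Visit 2 data from everyone dosed may be added as a sensitivity analysis, stating that it is unbiased only if progression depends on recorded Visit 2 data.

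The cost is one split table, one paired interval, one disposition category and some edits to the text. The glucose data are already collected. The downside is a little more analysis work and a paired estimate that is not itself free of selection.

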3.2 Study Duration

Two individual doses of Afrezza will be administered during the study, during Visits 2 and 3. The duration of each subject's participation in the trial is expected to be approximately 2 weeks.

The end of the clinical study is defined as the day the last subject completes his/her last visit. The length of the entire study (from the first subject enrolled to the last subject last visit) is expected to be approximately 3 months.

3.3 Selection of Study Population

The population sought for this study is adult subjects ≥ 18 years of age with T1DM or T2DM. No more than 50% of subjects enrolled will have T2DM. Twenty subjects are planned to complete the study. Subjects who do not complete the study may be replaced.

Specific inclusion and exclusion criteria are detailed in Section 3.3.1 and Section 3.3.2.

3.3.1 Inclusion Criteria

Subjects must meet all of the following inclusion criteria to be eligible to participate in the study:

At screening:

1. Subjects ≥ 18 years of age at the time of signing the informed consent form
2. Clinical diagnosis of T1DM or T2DM (per the Investigator) and on a stable basal-bolus insulin regimen

3.3.2 Exclusion Criteria

Subjects meeting any of the following exclusion criteria at screening will not be enrolled in the study.

1. History of asthma, chronic obstructive pulmonary disease, or any other clinically important pulmonary disease (e.g., cystic fibrosis, bronchopulmonary dysplasia), use of any medications to treat such conditions within the last year, or significant congenital or acquired cardiopulmonary disease
2. History of serious complications of diabetes (e.g., active proliferative retinopathy or symptomatic autonomic neuropathy)
3. On dialysis
4. Respiratory tract infection within 14 days before screening (subject may return 14 days after resolution of symptoms for rescreening)
5. Treatment with any investigational drug in the past 30 days or an investigational device in the past 2 weeks
6. Any disease other than diabetes or initiation of any new medication that, in the judgment of the Investigator, could have a direct impact on glycemic control during the study
7. Use of antiadrenergic drugs (e.g., beta blockers and clonidine)
8. Any concurrent illness (other than diabetes mellitus) not controlled by a stable therapeutic regimen
9. History of a significant eating disorder (e.g., anorexia or bulimia nervosa)
10. Current drug or alcohol abuse or a history of drug or alcohol abuse that, in the opinion of the Investigator or the Sponsor, would make the subject an unsuitable candidate for participation in the study
11. History of smoking (includes cigarettes, cigars, pipes, vaping devices, and marijuana) in the 6 months before screening
12. Female subject who is pregnant, breastfeeding, intends to become pregnant, or is of child-bearing potential and not using adequate contraceptive methods as required by local regulation or practice (may include sexual abstinence)
13. An event of severe hypoglycemia, as judged by the Investigator, within the 90 days before screening
14. An episode of DKA requiring hospitalization within the 90 days before screening

15. Exposure to Afrezza in the 30 days before screening

Subjects who are unable to comply with the requirements of the study or who, in the opinion of the Investigator, should not participate in the study are not eligible. In addition, any subjects for whom Afrezza is contraindicated, based on the Afrezza PI ([Afrezza 2020](#)), should not be enrolled in the study.

3.3.3 Removal of Subjects from Therapy or Assessment

A subject will be considered to have completed the study when the subject completes the treatment visits and the follow-up visit assessments.

If a subject discontinues from the study before completing all protocol-specified visits, an early-termination visit should be conducted as soon as possible to have the assessments shown in the Schedule of Assessments ([Table 2](#)).

Participation in the study is strictly voluntary. A subject or legally authorized representative has the right to withdraw from the study at any time and for any reason. If he/she chooses to withdraw, the Investigator must be informed immediately. The Investigator has the right to terminate participation of any subject at any time if the Investigator deems it in the subject's best interest. The Investigator should discuss the subject's withdrawal with the medical monitor beforehand, if possible. If not possible, the Investigator should discuss the withdrawal with the medical monitor within 24 hours of being informed of the decision.

For any subject who fails to return to the site, the Investigator should make every effort to contact the subject (e.g., contact the subject's family or private physician, review available registries or health care database) and to determine their health status. Attempts to contact the subject must be documented in the subject's study records (e.g., times and dates of attempted telephone contact, receipt for sending a registered letter, and a copy of the letter).

Subjects withdrawn from the study must not be re-enrolled in the study. Their identification numbers must not be reused.

3.3.3.1 Reasons for Discontinuation

The reason and circumstances for early termination will be documented in the subject's case report form (CRF). The reason for any early discontinuation should be indicated on this form. The primary reason for a subject's early study termination should be selected from the following standard categories of early termination:

- *Adverse Event:* Clinical or laboratory events occur that, in the medical judgment of the Investigator could affect the subject's safety or well-being if treatment is continued. This includes serious ([Section 4.1.2](#)) and nonserious AEs regardless of relation to the study drug.
- *Withdrawal of Consent:* The subject desires to withdraw from further participation in the study in the absence of an Investigator-determined medical need to withdraw. If the subject gives a reason for withdrawing, it should be recorded in the CRF.

- *Major Protocol Violation:* The subject's findings or conduct fails to meet the protocol entry criteria or fails to adhere to the protocol requirements that are deemed to affect subject safety or the integrity of the study data.
- *Pregnancy:* The subject becomes pregnant.
- *Smoking:* The subject begins smoking or vaping, including smoking marijuana.
- *Lost to Follow-up:* The subject stops coming for visits and study personnel are unable to contact the subject.
- *Other:* The subject discontinues from the study for a reason other than those listed above, such as termination of study by Sponsor.

If a subject discontinues from the study due to the ongoing severe acute respiratory syndrome coronavirus 2 (SARS-CoV-2) global pandemic, information should be captured on the CRF so this information can be summarized in the clinical study report at the end of the study, in line with the FDA Guidance on Conduct of Clinical Trials of Medical Products during COVID-19 Public Health Emergency ([FDA 2021](#)). The reason for discontinuation should be recorded on the CRF as SARS-CoV-2/coronavirus 2019 (COVID-19), if applicable, and include as many details as possible.

For example, specific reasons may include, but are not limited to:

- The subject exhibits symptoms consistent with COVID-19 within the last 10 days (yes/no).
- The subject has a positive test result for SARS-CoV-2 (yes/no).
- The subject has neither symptoms nor a positive test but has chosen to discontinue treatment due to COVID-19 concerns.

